### 6.1. Subject Enrollment and Treatment Assignment

Subject eligibility will be established at the conclusion of the screening evaluations. The screening number and/or subject ID will be assigned for that individual subject by the designated IWRS. Subject eligibility must be determined by results received from the central lab with exceptions made for re-screening and human epidermal growth factor receptor 2 (HER2) testing as described in Sections [6.2.2](#) and [6.2.8.2](#).

It is the responsibility of the investigator to ensure that each subject is eligible for the study before randomization. A subject will be considered enrolled once he or she has completed randomization.

Subjects in both treatment arms will undergo all the same procedures. Details regarding randomization and treatment assignment are in Section [5](#).

### 6.2. Study Procedure Descriptions

The sections below describe the individual study procedures outlined in subsequent sections and the schedule of assessments. During the treatment period, all visits may be performed within the windows identified in [Appendix 2](#).

#### 6.2.1. Informed Consent

All subjects must sign and date the most recent IRB/IEC-approved informed consent form before any study specific procedures are performed except where noted in the protocol in relation to standard of care procedures. **CCI**

### **6.2.2. Re-Screening Criteria**

Subjects who do not randomize within 28 days of screening will be screen failed. The screening period may be extended beyond 28 days with sponsor approval if the only outstanding eligibility criterion is the human epidermal growth factor receptor 2 (HER2) status.

Re-screening may be allowed. Subjects who are re-screened after 30 days, must be re-consented with a new screening number, and repeat the screening assessments. For subjects re-screened within 30 days, assessments with results that would exclude the subject will need to be repeated. Subjects with abnormal electrolyte values during screening will be allowed to repeat testing for the purposes of study eligibility - replacement therapy is permitted. If this is the only inclusion/exclusion criteria not met, these analytes may be retested (locally or centrally) so that values above the lower limit of normal could be achieved without the need to screen fail the subject.

Subject eligibility must be determined by results received from the central lab. However, if there have been 2 failed attempts to obtain test results from the central lab, eligibility may be determined using local lab results, with documentation of failed attempts, local lab results, and sponsor approval.

### **6.2.3. Medical & Medication History**

A complete medical and surgical history will be obtained by the investigator or designee at screening, including disease history, and recorded on the eCRF.

All medications taken within 30 days prior to screening and during the screening period will be obtained prior to randomization and recorded on the eCRF. At each study visit, the site will capture any and all medications taken by the subject since the last visit or during the visit (as applicable). Concomitant medications include prescription and non-prescription medications, vitamins and minerals.

In addition, supportive therapies given during the course of the study (eg, blood transfusion, growth factor) should be collected and recorded on the eCRF.

### **6.2.4. Physical Examination**

A physical examination (PE) will be performed at screening, end of treatment (EOT) and EOS. This will include assessment of clinical signs and symptoms. The exam will be performed by a physician, a physician's assistant, or nurse practitioner qualified to perform assessments. Breast, genital, and rectal examinations are not required, unless warranted in opinion of the healthcare provider.

A modified physical exam capturing changes from prior exams will be performed at Day 1 of each cycle and at the 30-day Safety Follow-Up. Height will be collected at Screening only and entered in the CRFs in centimeters. Body surface area (BSA) to determine the dose for mFOLFOX6 will be calculated using height and weight; the Mosteller formula:  $\sqrt{[\text{Height (cm)} \times \text{Weight (kg)}] / 3600}$  is preferred. However, institutional guidelines/practice for calculating BSA will also be allowed.

### **6.2.5. Vital Signs & Weight**

Vital signs ie, blood pressure, heart rate, respiratory rate, and oral temperature, will be measured by the investigator or qualified designee as per standard institutional guidelines at each study visit as indicated in [Appendix 2](#). Weight will be collected at the same visits vital signs are taken and entered in the CRFs in kilograms. BSA to determine the dose for mFOLFOX6 will be calculated using weight in kilograms. The Mostellar formula is preferred for calculating BSA. However, institutional guidelines/practice for calculating BSA will also be allowed.

### **6.2.6. Electrocardiogram Assessment**

A single 12-lead electrocardiogram (ECG) will be collected at Screening, Day 1 of each cycle, at the EOT and EOS visits, per standard practice. Additional ECGs following administration of oxaliplatin will be collected at visits when oxaliplatin is administered after the infusion is completed (i.e., Days 1 and 15 of each cycle, up to a maximum of six 28-day cycles) as required per country label guidance regarding cardiac monitoring. The investigator will review all ECGs and retain the tracing with the source documents. ECGs obtained after oxaliplatin infusions must be reviewed by the investigator/sub investigator before subjects leave the clinic/infusion center.

### **6.2.7. Performance Status**

Performance status will be scored using the ECOG performance status scale index (refer to [Appendix 4](#)), at Screening, Day 1 of each cycle, EOT, EOS and 30-day Safety Follow-up visits. ECOG used to determine eligibility must be the performance status during the screening period. ECOG performance status on Cycle 1 Day 1 may be waived if it was conducted during screening within 4 days of Cycle 1 Day 1.

### **6.2.8. Laboratory Assessments**

The central laboratory will be responsible for chemistry, hematology, coagulation, urinalysis, and serum pregnancy testing (per [Table 6-1](#)) as well as processing and/or storage of other study samples. Specific instructions for processing, labeling, and shipping samples will be provided in a central laboratory manual. The date and time of sample collection will be reported to the central laboratory.

If central laboratory results are not available, local laboratories may be used for dosing decisions. Local laboratory assessments resulting in a dose change or as part of an adverse event assessment, which is not supported by central lab results, will be reported on the eCRF.

Urine pregnancy test will be performed at the site.

**Table 6-1. Analytes**

Chemistry	Urinalysis	Hematology	Other
Albumin	Color and appearance	WBC	Serum $\beta$ -hCG or urine pregnancy test c
Alkaline phosphatase	Specific gravity	Hemoglobin	
ALT	pH	Hematocrit	
AST	Occult blood	Platelet	
Bicarbonate	Protein	ANC	
BUN	Glucose		
Calcium	Bilirubin	Differential	
Chloride	Leukocyte esterase	Eosinophils	
Creatinine a	Nitrite	Lymphocytes	
Glucose	Urobilinogen	Monocytes	
Lipase	Ketones	Neutrophils	
Magnesium	Microscopic b		
Phosphorus		Coagulation	
Potassium		PT/INR	
Sodium		aPTT	
Total bilirubin			
Direct bilirubin			
Total protein			
CA19-9			
CEA			

ANC = absolute neutrophil count; ALT = alanine aminotransferase; aPTT = Activated Partial Thromboplastin Time; AST = aspartate aminotransferase; BUN = blood urea nitrogen; CEA=carcinoembryonic antigen;  $\beta$ -hCG = beta-human chorionic gonadotropin; HER2 = human epidermal growth factor receptor 2; INR = International Normalized Ratio; PT = Prothrombin Time; SGOT = Serum Glutamic-Oxaloacetic Transaminase; SGPT = Serum Glutamic-Pyruvic Transaminase; WBC = white blood cell

a Estimated creatinine clearance ( $CL_{cr}$ )/glomerular filtration rate will be calculated based on the Cockcroft-Gault formula using actual body weight:  $CL_{cr}$  (mL/min) =  $(140 - \text{age} [\text{years}]) * \text{weight} (\text{kg}) / (\text{serum creatinine} [\text{mg/dL}] * 72)$ . If the subject is female, multiply the quantity by 0.85.

b Reflex testing based on other abnormalities

c Females of child-bearing potential only. Serum pregnancy will be conducted at Screening. Urine pregnancy will be conducted pre-dose on Day 1 of each cycle

Screening laboratory samples should be obtained within 28 days prior to randomization. Blood samples will be obtained for hematology, chemistry, coagulation, and pregnancy testing for female subjects. A urine sample will also be obtained at screening for urinalysis.

Blood samples for hematology and chemistry will be obtained at pre-dose of Days 1 and 15 of each cycle, EOT, EOS, and 30-day Safety Follow-up. A urine sample for urinalysis and pregnancy testing for female subjects will also be obtained at Day 1 of each cycle, EOT, EOS, and 30-day Safety Follow-up (urinalysis only). Blood samples for coagulation will be obtained at EOT and EOS.

At any time during the study, abnormal laboratory parameters that are clinically relevant (eg, lead to clinical symptoms or signs, require therapeutic intervention), and constitute an AE must be recorded in the eCRF.

#### 6.2.8.1. Pregnancy Test

All females of childbearing potential (see [Appendix 3](#)) will have a serum pregnancy test at screening. Urine pregnancy tests will be performed on Day 1 of every cycle, EOT, EOS, and 30-day Safety Follow-up.

#### 6.2.8.2. Human Epidermal Growth Factor Receptor 2 (HER2) Testing

Prior to randomization, the subject's tumor should have been tested for HER2 status with approved immunohistochemistry (IHC) and in situ hybridization (ISH) kits. HER2 positivity is defined as IHC3+ or IHC2+/ISH+ (ISH positivity is defined as HER2:CEP17 ratio of  $\geq 2.0$ ). Results for HER2 status obtained prior to signing informed consent are acceptable if obtained with approved IHC and ISH kits. HER2 status may be determined during screening by testing the tumor at the central lab or a local lab with approved IHC and ISH kits.

#### 6.2.8.3. Archival Tumor Tissue

Archival tumor tissue formalin-fixed paraffin embedded (FFPE) blocks will be collected from all subjects for biomarker analysis and shipped to central laboratory for sectioning after Day 1 of Cycle 1. If FFPE blocks are not available, unstained slides are also acceptable (see Covance manual for details). If an archival block was submitted for HER2 testing, and the subject is randomized, the block will be stored for biomarker analysis. However, if slides were submitted for HER2 testing, additional slides will be required after Day 1 of Cycle 1 for biomarker analysis.

#### 6.2.8.4. Anti-GS-5745 Antibody

Blood samples for anti-GS-5745 antibody will be collected prior to dosing on Day 1 of cycles 1, 2, 3, 5, 7, and every 3 cycles thereafter, at the EOT, EOS, and 30-Day Safety Follow Up visits.

#### 6.2.8.5. GS-5745 Pharmacokinetics

Blood plasma samples will be collected for GS-5745 PK at 30 ( $\pm 15$ ) minutes after the end of infusion on Cycle 1 Day 1, prior to dosing, and 30 ( $\pm 15$ ) minutes after the end of infusion on Day 1 of Cycles 2, 3, 5, 7, and every 3 cycles thereafter, at the EOT and EOS visits.

#### 6.2.8.6. Optional PK Sub-study

CCI  
[Redacted text block]

#### 6.2.8.7. Biomarkers

Samples for biomarker analysis as listed on [Table 3-1](#) will be collected as specified below and in [Appendix 2](#):

- Blood biomarker samples will be collected prior to dosing on Cycle 1 Day 1, Cycle 1 Day 15, and Day 1 of Cycles 2 and 4, and every 2 cycles thereafter.
- A pharmacodynamic biomarker sample and immune-monitoring sample will be collected prior to dosing on Cycle 1 Day 1 and Cycle 3 Day 1.
- A biomarker sample for circulating tumor DNA will be collected prior to dosing on Cycle 1 Day 1, Cycle 3 Day 1, and at disease progression.

- CCI [REDACTED]

#### 6.2.8.8. Core Biopsy

At disease progression, a core biopsy will be collected (fine needle aspirate is not acceptable) if medically feasible. The sample should be collected by the last clinic visit on study, ie, EOS or 30-Day Safety Follow-up visit.

### 6.2.9. Disease and Response Assessment

#### 6.2.9.1. Tumor Imaging

Either contrast-enhanced CT or gadolinium-enhanced MRI of the chest, abdomen, and pelvis will be performed at screening, every 8 weeks during the study (starting from Cycle 1 Day 1) and at the EOS visit if one has not been performed within the last 8 weeks. Tumor burden will be evaluated solely based on radiographic imaging per RECIST v 1.1. Chest x-ray, ultrasound, endoscopy, laparoscopy, positron-emission tomography, radionuclide scans, or tumor markers will not be considered for response assessment.

For radiographic evaluations, the same method of assessment and the same technique (eg, scan type, scanner, subject position, dose of contrast, injection/scan interval) should be used to characterize each identified and reported lesion at baseline and during study treatment and follow-up.

Scans taken as part of standard medical practice up to 42 days prior to randomization can be used for Screening as long as they meet all study requirements. During the treatment phase, scans may be performed at time points other than every 8 weeks as clinically indicated to assess tumor progression.

For subjects who stop study treatment in the absence of disease progression (eg, experienced unexpected toxicity), scans should continue to be collected approximately every 8 weeks until disease progression or initiation of systemic anti-tumor therapy other than the study treatment, whichever is earlier.

All relevant clinical and radiographic information required to make each assessment must be made available for source verification and submission to a central reader. Scans will be transferred to a central reader for collection and future analysis. Disease progression will be determined by the investigator or qualified designee.

#### **6.2.10. Patient-reported Outcomes Assessments**

Patient-reported outcomes (PRO) will be collected at Day 1 of each cycle, EOT and EOS visits, and at the 30 day safety follow up visit prior to any assessments in the clinic.

##### **6.2.10.1. EuroQol-5D**

The EuroQol-5D (EQ-5D) is a general health quality of life self-report instrument that assesses 5 dimensions: mobility, self-care, usual activities, pain/discomfort, and anxiety/depression. Each dimension has 3 levels (EQ-5D-3L), ranging from no health problem, moderate health problem(s), and extreme health problem(s). It also includes a single visual analog scale for assessment of current general health.

##### **6.2.10.2. Quality of Life Questionnaire**

The European Organization for Research and Treatment of Cancer (EORTC) Quality of Life Questionnaire (QLQ-C30) is a self-report questionnaire consisting of 30 questions assessing 15 sections of the subject's wellbeing. The accompanying module for gastric cancer, QLQ-STO22, has an additional 22 questions.

#### **6.2.11. Study Drug and Chemotherapy Administration**

Study drug (GS-5745/placebo) will be dosed on Days 1 and 15 of every 28-day cycle via intravenous infusion over approximately 30 ( $\pm$  5) minutes followed by chemotherapy (mFOLFOX6) as described in Section 5. One cycle of mFOLFOX6 consists of 2 infusions.

#### **6.2.12. Adverse Events**

From the time of obtaining informed consent through the first administration of study drug, record all SAEs as well as any AEs related to protocol-mandated procedures on the AE eCRF. All other untoward medical occurrences observed during the screening period, including exacerbation or changes in medical history are to be captured on the medical history eCRF.

From the time of the first administration of study drug through 55 days post the last administration of treatment (GS-5745/placebo and mFOLFOX6), record any SAEs, and AEs including exacerbation or changes in medical history, on the AE eCRF.

See Section 7 Adverse Events and Toxicity Management for additional details.

### **6.3. Assessments for Premature Discontinuation from Study**

If a subject has discontinued all study treatments prior to definitive disease progression, the subject shall remain on study for follow-up for progression-free survival (see Sections 3.5 and 3.6). Every attempt should be made to keep the subject in the study and continue to perform tumor evaluation by CT or MRI every 8 weeks. Subjects will remain on study until disease progression or initiation of non-study specific anti-neoplastic therapy in the absence of progression, whichever occurs earlier.

If it is not possible to keep the subject on study, or acceptable to the subject or investigator, the subject may be withdrawn. It is recommended that the investigator consults with the medical monitor prior to removing the subject from study for any reason except subject withdrawal of consent.

### **6.4. Criteria for Discontinuation of Study Treatment**

See Sections 3.4 and 3.6 for discontinuation criteria.

### **6.5. End of Treatment**

End of treatment (EOT) assessments will be completed only by subjects who discontinue all treatment prior to disease progression. These assessments should be completed as soon as possible after the decision is made. Every attempt should be made to keep the subject in the study and continue to perform tumor evaluation by CT or MRI every 8 weeks until disease progression.

### **6.6. End of Study**

End of study (EOS) assessments will be completed when the subject meets at least 1 of the criteria for study discontinuation (Section 3.6).

### **6.7. Safety Follow-Up**

A follow-up visit will be performed 30 days ( $\pm 7$  days) following the last dose of GS-5745/placebo or all components of mFOLFOX6, whichever is discontinued later. A follow-up phone call will be performed 55 days ( $\pm 7$  days) following the last dose of GS-5745/placebo or all components of mFOLFOX6, whichever is discontinued later to assess any AEs and concomitant mediations.

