### 7.3.1. Adverse Events

Following initiation of study medication, collect all AEs, regardless of cause or relationship, until 55 days after last administration of GS-5745/placebo or all components of mFOLFOX6, whichever is discontinued later. These must be reported to the eCRF database as instructed.

All AEs should be followed up until resolution or until the adverse event is stable, if possible. Gilead Sciences may request that certain AEs be followed beyond the protocol defined follow-up period.

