### 7.3.2. Serious Adverse Events

All SAEs, regardless of cause or relationship, that occurs after the subject first consents to participate in the study (ie, signing the informed consent) and throughout the duration of the study, including the protocol-required post treatment follow-up period, must be reported to the eCRF database and Gilead DSPH as instructed. This also includes any SAEs resulting from protocol-associated procedures performed after informed consent is signed.

Any SAEs and deaths that occur after the post treatment follow-up visit but within 55 days of the last dose of GS-5745/placebo or all components of mFOLFOX6, whichever is discontinued later, regardless of causality, should also be reported.

Investigators are not obligated to actively seek SAEs after the protocol defined follow up period, however, if the investigator learns of any SAEs that occur after study participation has concluded and the event is deemed relevant to the use of study drug, he/she should promptly document and report the event to Gilead DSPH.

- All AEs and SAEs will be recorded in the eCRF database within the timelines outlined in the eCRF completion guideline.
- SAEs will be reported using an electronic SAE (eSAE) system.

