##### **8.3.1.2. Safety Analysis Set**

The safety analysis set will include data from all subjects who receive  $\geq 1$  dose of study treatment, with treatment assignments designated according to the actual treatment received.

This analysis set will be used in the analysis of safety variables as well as study treatment administration. All data collected up to the last dose of GS-5745/placebo or mFOLFOX6 or 5-FU and LV, whichever is later, plus 55 days will be included in the safety summaries.

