Collect archival tumor tissue for biomarker testing o		X														

Study Phase	Screening	Randomization Cycle 1	Cycle 1	Each Cycle (28 days)		Cycle 2 (PK/Antibody/ Biomarker)	Cycle 3 (PK/Antibody/ Biomarker)	Cycle 4 & every 2 cycles (PK/Antibody/ Biomarker)	Cycle 5, 7 & Every 3 Cycles (PK/Antibody/ Biomarker)	EOT r	Every 8 weeks	Disease Progression	EOS s	30-day Safety Follow-up t	55-day Safety Follow-Up u	5-year Long Term Follow-Up
Cycle Day		1 a	15	1	15	1 h, i, j, k , 2 i , 8 i , 15 i	1	1	1	N/A	N/A	N/A	N/A	N/A	N/A	
Window (day)	-28		±3	±3	±3	±3	±3	±3	±3		±7		±7	±7	±7	N/A
CT or MRI & Treatment Response Assessment p	X										X		X			
Core Biopsy q												X				
Overall Survival and Other Antitumor Therapy																X (Every 3 months)

- a Cycle 1 Day 1 (C1D1) must occur within 3 days following randomization.
- b Complete physical examination (PE) to be performed at Screening, EOT and EOS. A modified PE capturing changes from prior exams will be performed at subsequent visits. Height is required at Screening only.
- c ECOG performance status on Cycle 1 Day 1 may be waived if has been conducted during screening within 4 days of Cycle 1 Day 1.
- d Adverse events will be assessed at each clinic visit from Screening up to and including the 55-day Safety Follow-up visit. Concomitant medications will be recorded at each clinic visit from Screening up to and including the 55-day Safety Follow-up visit or EOS visit whichever is later.
- e Study drug (GS-5745/placebo) will be dosed on Days 1 and 15 of each cycle over 30 (± 5) min. Chemotherapy (mFOLFOX6) will be administered after study drug and will consist of l-LV 200mg/m^2 or dl-LV 400mg/m^2 and oxaliplatin 85 mg/m^2 followed by bolus 5-FU 400mg/m^2 and a 46 hour infusion of 5-FU 2400 mg/m^2. After 6 cycles of mFOLFOX6, the oxaliplatin component will be discontinued. Leucovorin and 5-FU will be continued as maintenance therapy, in combination with GS-5745/placebo, in the absence of disease progression or toxicity warranting discontinuation of therapy.
- f If applicable (females of child bearing potential). Serum pregnancy testing will be conducted at Screening. Urine pregnancy testing will be conducted pre-dose on Day 1 of each cycle, at EOT, and EOS.

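### The call that closes adverse-event collection may be made from Day 48, so up to 7 days of the stated 55-day period can go unasked when the call is early and no later on-study contact follows

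*Protocol*

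**What the plan says.** **Collection period.** Protocol Section 6.2.12 has AEs recorded "through 55 days post the last administration of treatment". Section 7.3.1 tells sites to "collect all AEs, regardless of cause or relationship, until 55 days after last administration of GS-5745/placebo" or of all mFOLFOX6 components, counting from the later of the two. For SAEs and deaths, Section 7.3.2 adds a reporting duty: "Any SAEs and deaths that occur after the post treatment follow-up visit but within 55 days of the last dose" are to be reported whatever their cause.

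**Analysis period.** Section 8.3.1.2 counts from the last dose of study drug or chemotherapy, "whichever is later, plus 55 days will be included in the safety summaries". Section 8.6 uses the same period. The treatment-emergent definition in Section 8.6.2 also runs to 55 days, but from permanent discontinuation of study drug. SAP Section 7.1.5.1 counts 55 days from the end of andecaliximab/placebo, or 30 days from the end of all study treatment.

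**Closing contact.** Section 6.7 provides for it in these words: "A follow-up phone call will be performed 55 days" after treatment ends. The full timing is "55 days ( $\pm 7$ days) following the last dose" of whichever treatment stops later, and the call's purpose is to ask about AEs and concomitant medications. The window row of Appendix 2 gives the same 7 days on either side. Footnote d of Appendix 2 makes this the end of AE assessment: "Adverse events will be assessed at each clinic visit from Screening up to and including the 55-day Safety Follow-up visit".

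**Afterwards.** Under Section 6.8, the long-term follow-up calls every 3 months record survival status, other anti-cancer therapy and cancer-related surgery. They do not ask about AEs.

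**The concern.** A contact that closes an ascertainment period should not come before the period ends. Here it can, by as much as a week. An AE that starts after an early call but by Day 55 is inside the collection and summary period, yet no scheduled question would bring it to light. Nothing in the protocol requires a second call when the first is early.

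Comparing safety is a stated secondary objective (Section 2.2). With the present window, the actual end of active ascertainment varies by subject and site from Day 48 onward, while the summaries use a common Day 55. Days on which nobody asked would be treated like days on which nothing happened.

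**Working it through.** This is calendar arithmetic. The documents state no figure for the gap, so there is none to reproduce.

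**Inputs.** Nominal call day 55 and window of 7 days either side (Section 6.7, Appendix 2). End of collection on Day 55 (Sections 6.2.12 and 7.3.1). Days are counted from the last dose of the later-stopped treatment.

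**Permitted call days.** Earliest 55 − 7 = 48; latest 55 + 7 = 62. That is 15 possible days.

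**Unasked days for a call on day c:** gap = max(0, 55 − c).

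- Calls on Days 48, 49, 50, 51, 52, 53 and 54 leave 7, 6, 5, 4, 3, 2 and 1 days.
- Calls on Days 55 to 62 leave 0 days.

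So 7 of the 15 permitted days create a gap, and only Day 48 loses the whole week.

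**Size.**

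- Worst case: 7/55 = 12.7% of the post-treatment period.
- Assuming calls spread evenly over the 15 days (the documents give no distribution): (7 + 6 + 5 + 4 + 3 + 2 + 1)/15 = 28/15 = 1.9 days over all calls, or 28/7 = 4 days among the early ones.

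**Who has no later contact.** Progression stops treatment (Section 3.4) and also ends study participation, after which the subject moves to long-term follow-up (Section 3.6). For a subject who stops for that reason, no scheduled AE question follows the call.

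**Under the SAP's treatment-emergent definition.** Let k be the number of days by which the last chemotherapy dose follows the last andecaliximab/placebo dose. The call is timed from the later dose, while the SAP's 55 days run from the earlier one. Measured from the later dose, the SAP window ends at max(55 − k, 30). With a Day 48 call, the gap is max(0, 55 − k − 48) = max(0, 7 − k). For k = 0 it is 7 days, and for k of 7 or more it is 0. Section 5.3.1.1 allows chemotherapy to continue after study drug stops, so k can be large. Progression stops both treatments (Section 3.4), and stopping all mFOLFOX6 components also stops study drug (Section 5.3.1.2). In those cases k can be near 0 and the gap lies inside the SAP window too.

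**The case against.** The strongest reply is that the duty to collect runs to Day 55 whatever the date of the call, and that the events that matter most are covered elsewhere. Much of this stands.

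- **Serious events.** Section 7.3.2 requires SAEs and deaths within 55 days to be reported, and deaths also surface through survival follow-up. This narrows the gap mainly to new non-serious AEs. It does not close it, because a duty to report is not a scheduled question and Section 7.3.1 covers all AEs.
- **Later contacts.** Subjects who stop treatment before progression stay on study (Sections 3.5 and 6.3). Appendix 2 marks the combined AE and concomitant-medication row at the 8-weekly, progression and end-of-study columns, and these can fall after Day 48. That stands for those subjects. Footnote d weakens it somewhat: it extends concomitant medications to the end-of-study visit if that is later, but gives AEs no such extension. Subjects whose participation ended at progression have no such contacts.
- **SAP window.** For subjects whose chemotherapy outlasted study drug by at least 7 days, the SAP's 55-day window is fully covered even by a Day 48 call. SAP Section 7 also summarizes data through completion of follow-up rather than to a fixed day. This limits the effect on treatment-emergent tables but does not remove the mismatch inside the protocol.
- **Scale.** If treatment lasted about the assumed control median PFS of 9 months (Section 8.11), AE observation would total about 9 × 30.4375 + 55 = 329 days. The worst case is then 7/329, about 2%, and the even-spread mean 1.9/329, about 0.6%. This is fair as context, though the post-treatment period is what the call exists to cover.

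A reader might go further and infer that last-week AEs are never asked about in this trial, or that the safety comparison is biased. The documents do not support either. Calls on 8 of the 15 permitted days cover the full period. The trial is double-blind, and Section 6.1 has both arms follow identical procedures. No mechanism for unequal ascertainment appears, and the number of missed AEs cannot be estimated from the text.

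**Conclusion.** The concern holds in limited form. The call window and the 55-day collection period do not agree. When the call is made on Days 48 to 54 and no later on-study contact occurs, 1 to 7 days of the stated period go unsolicited.

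The expected consequence is modest, non-differential under-ascertainment, mostly of new non-serious AEs. The ceiling of 12.7% needs no assumption beyond a Day 48 call; the 1.9-day mean depends on evenly spread calls. A share of 7 in 25 days (28%), counting only Days 31 to 55, could also be computed, but it fixes the 30-day visit at exactly Day 30 although that visit has its own 7-day window on either side, so it should not be relied on.

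Sample size, power and type I error are untouched. The point is worth correcting because a stated rule lets ascertainment close before the stated period ends, and the correction is nearly free.

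**What to change.** In Protocol Section 6.7 and in the window row of Appendix 2, change the 55-day call window from 7 days either side to 0/+7 days. State that the call asks about AEs with onset up to and including Day 55. Permitted calls then fall on Days 55 to 62 and the gap is max(0, 55 − c) = 0 for all of them.

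The cost is small. The same call is made, up to 7 days after the nominal date, with no added contact and no change to any treatment rule. It does need a minor protocol modification with ethics approval (Section 9.2.1) across approximately 188 planned centers, so it is best bundled with another amendment if one is due.
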